Appendix 2: Schedule of Pharmacokinetic and PD Biomarker Samples (cont.)

Table 1 All Cohorts (cont.)

| Study Visit | | Plasma Idasanutlin PK Sample | Serum MIC-1 Sample | Plasma Cytarabine PK Sample | Plasma Daunorubicin PK Sample |
|---------------------------|-------|---|---|---|---|
| Induction Cycle 1 (cont.) | Day 5 | Pre-idasanutlin administration (any time prior to dose on that day) | Pre-idasanutlin administration (any time prior to dose on that day) | Pre-idasanutlin administration (any time prior to dose on that day) | Pre-idasanutlin administration (any time prior to dose on that day) |
| | | 30 (±10) min after end of daunorubicin infusion | 30 (±10) min after end of daunorubicin infusion | | |
| | | 3 hr (±20 min) post-idasanutlin administration | 3 hr (±20 min) post-idasanutlin administration | | |
| | | 6 hr (±20 min) post-idasanutlin administration | 6 hr (±20 min) post-idasanutlin administration | | |
| | | 9 (±1) hr post-idasanutlin administration | 9 (±1) hr post-idasanutlin administration | | |
| Consolidation Cycle 1 | Day 1 | Pre-idasanutlin administration (any time prior to dose on that day) | | Pre-idasanutlin administration (any time prior to dose on that day) | |
| | | 3 hr (end of cytarabine infusion) | | 3 hr (end of cytarabine infusion) | |
| | | 6 hr (±20 min) post-idasanutlin administration | | 6 hr (±20 min) post-idasanutlin administration | |

PK=pharmacokinetic.

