Table 1 Treatment during the Dose-Escalation Phase

| Cycles | Drug Regimens |
|---|--|
| Induction Up to 2 cycles ^a | 
 • Cytarabine 200 mg/m² IV on Days 1–7 • Daunorubicin 60 mg/m² IV on Days 1–3 • Idasanutlin TBD QD (starting dose 200 mg) orally on Days 1–5 |
| Chemotherapy consolidation or allo-HSCT (per investigator discretion): | |
| Chemotherapy Up to 4 cycles | 
 • Cytarabine 1.5 g/m² IV on Days 1–5 administered over 3 hours • Idasanutlin TBD ^b QD orally on Days 1–5 |
| Allo-HSCT | 
 • As per local guidelines |
| Maintenance Cycles 1–12 ^c | 
 • Idasanutlin 150 mg QD orally on Days 1–5 ^d |

allo-HSCT = allogenic hematopoietic stem cell transplant; QD=once a day; TBD=to be determined.

^a Cytarabine/daunorubicin doses/regimen can be lowered in the second cycle as per site guidelines.

^b Dose in consolidation will be determined by the Sponsor after determination of all available data. It will not exceed induction dose.

^c On the basis of safety, tolerability, and clinical benefit and after consultation with the Medical Monitor, intra-patient escalation may be allowed to 200 mg.

^d On the basis of safety, tolerability, and clinical benefit and after consultation with the Medical Monitor, patient may be allowed to continue maintenance at the same dose within past the 12 cycles

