4.3.2.3 Daunorubicin

Daunorubicin will be administered in induction at a dose of 60 mg/m² QD for 3 days as IV infusion, immediately after the corresponding dose of idasanutlin. Dose and regimen can be lowered per investigator choice in the second induction cycle.

The dose of daunorubicin should be calculated based on a body weight measurement within 2 days of the first day of each cycle. To calculate BSA for the daunorubicin dose, refer to [Appendix 9](#).

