Appendix 1: Schedule of Activities (cont.)

Table 1: Induction (cont.)

| Assessment/Procedure | Screening ^a | Induction (28-Day Cycle) up to 2 Cycles | | | | | | | | | | |
|---|------------------------|---|----|----|----|----|----|----|-----|-----|-----|-------------------|
| | Days –14 to –1 | D1 | D2 | D3 | D4 | D5 | D7 | D8 | D15 | D22 | D28 | |
| | | | | | | | | | | | | |
| EORTC QLQ-C30, EQ-5D-5L ^k | | x ^l | | | | | | | | | | |
| HMRA | | | | | | | | | | | | x ^f |
| Bone marrow sampling for HMRA ^m | x | | | | | | | | | | | x ^f |
| Bone marrow sampling ⁿ (MRD/Flow, EDTA, PAXgene [®]) | x | | | | | | | | | | | x ^f |
| Whole blood sampling (flow, EDTA, clinical) | x | x | | | | | | | | | | x ^{f, o} |
| Whole blood sampling PAXgene | | x | | | | | | | | | | |
| RBR sampling/blood serum and plasma (optional) | x | | | | | | | | | | | |
| PK sampling and MIC-1 | | Refer to Appendix 2 | | | | | | | | | | |
| Concomitant medications | x | To be recorded continually; see Section 4.4 | | | | | | | | | | |
| Adverse events | | To be assessed continually; see Section 5.3.1 | | | | | | | | | | |
| Daunorubicin treatment (60 mg/m ² IV) ^p | | x | x | x | | | | | | | | |
| Idasanutlin treatment (PO QD) ^p | | x | x | x | x | x | | | | | | |
| Cytarabine treatment (200 mg/m ² IV) ^p | | x | x | x | x | x | x | | | | | |

AML=acute myeloid leukemia; CT=computed tomography; CTCAE=Common Terminology Criteria for Adverse Events; ECHO=echocardiogram; ECOG=Eastern Cooperative Oncology Group; eCRF=electronic Case Report Form; EDTA=ethylenediaminetetraacetic acid; EOI=end of induction; EORTC=European Organisation for Research and Treatment of Cancer; EORTC QLQ-C30=EORTC Quality-of-Life Questionnaire–Core 30; EQ-5D-5L=EuroQol 5-Dimension, 5-Level; FACIT=Functional Assessment of Chronic Illness Therapy; HMRA=hematologic malignancy response assessment; MRD=minimal residual disease;

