|-------------------|-------|---|---|---|---|
| Induction Cycle 1 | Day 1 | Pre-idasanutlin administration (any time prior to dose on that day) | Pre-idasanutlin administration (any time prior to dose on that day) | Pre-idasanutlin administration (any time prior to dose on that day) | Pre-idasanutlin administration (any time prior to dose on that day) |
| | | 30 (±10) min after end of daunorubicin infusion | 30 (±10) min after end of daunorubicin infusion | 30 (±10) min after end of daunorubicin infusion | 30 (±10) min after end of daunorubicin infusion |
| | | 3 hr (±20 min) post-idasanutlin administration | 3 hr (±20 min) post-idasanutlin administration | 3 hr (±20 min) post-idasanutlin administration | 3 hr (±20 min) post-idasanutlin administration |
| | | 6 hr (±20 min) post-idasanutlin administration | 6 hr (±20 min) post-idasanutlin administration | 6 hr (±20 min) post-idasanutlin administration | 6 hr (±20 min) post-idasanutlin administration |
| | | 9 (±1) hr post-idasanutlin administration | 9 (±1) hr post-idasanutlin administration | 9 (±1) hr post-idasanutlin administration | 9 (±1) hr post-idasanutlin administration |
| | Day 3 | Pre-idasanutlin administration (any time prior to dose on that day) | Pre-idasanutlin administration (any time prior to dose on that day) | Pre-idasanutlin administration (any time prior to dose on that day) | Pre-idasanutlin administration (any time prior to dose on that day) |
| | | | 1.5 hr (±10 min) post-idasanutlin administration | | 1.5 hr (±10 min) post-idasanutlin administration |
| | | | 3 hr (±10 min) post-idasanutlin administration | | 3 hr (±10 min) post-idasanutlin administration |
| | | | 6 hr (±20 min) post-idasanutlin administration | | 6 hr (±20 min) post-idasanutlin administration |
| | | | 9 hr (±1 h) post-idasanutlin administration | | 9 hr (±1 h) post-idasanutlin administration |

PK=pharmacokinetic.

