Appendix 2: Schedule of Pharmacokinetic and PD Biomarker Samples (cont.)

Table 1 All Cohorts (cont.)

| Study Visit | | Plasma Idasanutlin PK Sample | Serum MIC-1 Sample | Plasma Cytarabine PK Sample | Plasma Daunorubicin PK Sample |
|--|-------|---|--------------------|---|-------------------------------|
| Consolidation Cycle 1 (cont.) | Day 5 | Pre-idasanutlin administration (any time prior to dose on that day) | | Pre-idasanutlin administration (any time prior to dose on that day) | |
| | | 1.5 hr (± 10 min) post-idasanutlin administration | | 1.5 hr (± 10 min) post-idasanutlin administration | |
| | | 3 hr (± 10 min) post-idasanutlin administration | | 3 hr (± 10 min) post-idasanutlin administration | |
| | | 6 hr (± 20 min) post-idasanutlin administration | | 6 hr (± 20 min) post-idasanutlin administration | |
| | | 9 (± 1) hr post-idasanutlin administration | | 9 (± 1) hr post-idasanutlin administration | |
| Maintenance Cycle 1 (expansion and post-consolidation) | Day 1 | Pre-idasanutlin administration (any time prior to dose on that day) | | | |
| | | 6 hr (± 20 min) post-idasanutlin administration | | | |

PK=pharmacokinetic.

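### The first post-dose idasanutlin and MIC-1 samples on Induction Cycle 1 Day 5 are timed from a daunorubicin infusion that is not given that day

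*Combined protocol and SAP*

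**What the plan says.** Appendix 2, Table 1 lists five samples on Induction Cycle 1 Day 5 for both plasma idasanutlin and serum MIC-1. They are pre-dose, then "30 (±10) min after end of daunorubicin infusion", then 3, 6 and 9 h after idasanutlin. Cytarabine and daunorubicin have a pre-dose sample only on that day.

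The regimen tables for dose escalation (Section 3.1.2.2, Table 1) and expansion (Section 3.1.3, Table 4) both give "Daunorubicin 60 mg/m² IV on Days 1–3". Section 4.3.2.3 states "Daunorubicin will be administered in induction at a dose of 60 mg/m² QD for 3 days as IV infusion". The daunorubicin row of the induction schedule (Appendix 1, Table 1) is marked on D1, D2 and D3 and on no later day. Idasanutlin does have a Day 5 dose: Table 1 gives "Idasanutlin TBD QD (starting dose 200 mg) orally on Days 1–5".

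On Day 5 of Consolidation Cycle 1 and of Maintenance Cycle 1, the early idasanutlin sample in Appendix 2 is set at "1.5 hr (± 10 min) post-idasanutlin administration".

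**The concern.** Section 4.5.8 directs that samples be collected according to Appendix 2 and stresses accurate recording of dosing and sampling times. A site cannot comply with this row. It can skip the draw, raise a query, or pick a time of its own.

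For idasanutlin, Induction Day 3 has a pre-dose sample only, so Day 5 is the only post-dose profile in induction after repeated dosing. Section 6.5 names maximum concentration and time to maximum concentration among the key parameters and plans to evaluate accumulation. The early part of the Day 5 curve informs these, and a sample that is not drawn cannot be recovered later. Day 5 is also where idasanutlin is profiled with 7+3 in induction, with cytarabine in consolidation and alone in maintenance, so a defined early time in each setting has value.

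**Working it through.** The check is a comparison of schedules, followed by simple counts.

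**1. Is there a Day 5 infusion to time from?** The daunorubicin days are {1, 2, 3} in Section 3.1.2, Section 3.1.2.2, Table 1, Table 4 and Appendix 1, Table 1; Section 4.3.2.3 says three days. The sampling day is 5. With once-daily dosing, the last infusion precedes the Day 5 idasanutlin dose by about (5 − 3) × 24 = 48 h. Read literally, 30 minutes after that infusion falls on Day 3.

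**2. Could an exception supply one?** The only flexibility is "Dose and regimen can be lowered per investigator choice in the second induction cycle" (Section 4.3.2.3). It is a lowering, and it applies to the second cycle. The samples at issue are in Cycle 1.

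**3. How do the other profiles in Appendix 2, Table 1 time the early sample?**

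| Day | Daunorubicin given? | Early idasanutlin sample | Early MIC-1 sample |
|---|---|---|---|
| Induction Cycle 1 Day 1 | Yes | 30 min after end of daunorubicin | 30 min after end of daunorubicin |
| Induction Cycle 1 Day 3 | Yes | None (pre-dose only) | 1.5 h after idasanutlin |
| Induction Cycle 1 Day 5 | No | 30 min after end of daunorubicin | 30 min after end of daunorubicin |
| Consolidation Cycle 1 Day 5 | No | 1.5 h after idasanutlin | None scheduled |
| Maintenance Cycle 1 Day 5 | No | 1.5 h after idasanutlin | None scheduled |

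The Day 5 entry repeats the Day 1 wording. On Day 1 it works, because daunorubicin is given. Induction Day 5 is the only day in the table timed from a drug not given that day. The entry stands under an explicit Day 5 label in two columns, so a table broken in conversion is an unlikely explanation.

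**4. Share of samples.** For each analyte, 1 of 4 post-dose timepoints (25%), or 1 of 5 counting pre-dose (20%), is undefined. The first post-dose time that can be taken as written is 3 h.

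**5. Patients.** Section 6.1 gives 9 to 15 evaluable patients in dose escalation, with an expected maximum of about 20 including 5 not evaluable, and about 40 in expansion.

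- Lower sum: 9 + 40 = 49.
- Upper sum: 20 + 40 = 60.
- Section 6.1 also says that the 20 favorable/intermediate-risk patients include dose-escalation patients already at the RP2D. If k patients count twice, the total falls by k. With k = 6, an assumption for illustration, the range is 43 to 54.

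These are upper figures, because some patients will not reach Day 5. The 30 post-consolidation patients receive no induction on study and are not affected.

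**The case against.** The contradiction itself is hard to dispute. The case on the other side is that little follows from it, and much of that case stands.

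- **Comparability.** A reader might infer that Day 5 exposure with 7+3 cannot be compared with Day 5 of consolidation and maintenance. The documents do not support that. Pre-dose, 3, 6 and 9 h are tied to idasanutlin in all three profiles, so four of five nominal times match. Idasanutlin doses may also differ between phases, which limits a direct comparison whatever the sampling. What is lost is the early phase.
- **Interaction objective.** A reader might infer that the assessment of interactions among the three drugs fails. Day 1 has a full five-sample profile for all three drugs with a valid anchor. On Day 5 cytarabine and daunorubicin have only a pre-dose sample. The objective does not rest on this row.
- **Population PK.** Section 3.3.3 plans population modelling with minimal sampling, and a sample taken at another time is usable if that time is recorded. This stands for samples that are drawn, not for those omitted.
- **Accepted gaps.** The plan itself takes the first post-dose idasanutlin sample at 3 h on Consolidation Day 1 and at 6 h on Maintenance Day 1. But those days are not the multiple-dose profile, and on Induction Day 5 the plan clearly meant to have an earlier sample.
- **Weight.** MIC-1 is a pharmacodynamic marker with a full Day 3 profile. Section 4.5.8.3 allows biomarker timepoints not critical for safety to be dropped. PK enters escalation decisions only where available.

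That sites will miss the sample or choose different times is a risk, not an outcome that the documents establish. A query from a site could also bring the error to light.

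**Conclusion.** The point holds as an internal inconsistency in an operative sampling row. One of four post-dose Day 5 timepoints, for idasanutlin and for MIC-1, cannot be taken as written in any patient who reaches Induction Cycle 1 Day 5. That is up to about 49 to 60 patients, and fewer with overlap at the RP2D. Nothing is fixed between pre-dose and 3 h in the only multiple-dose idasanutlin profile in induction. Estimates of Cmax and time to maximum concentration, and the early-phase comparison with later Day 5 profiles, are weakened to that extent.

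The conclusion rests on the daunorubicin schedule, which the protocol states consistently, and on the Day 5 row having been read correctly from the table. No primary endpoint, DLT assessment or sample size is touched. The documents do not say that 1.5 h was intended on Induction Day 5. That is an inference from neighbouring rows, so the sponsor has to confirm it.

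**What to change.** Reconcile the row with the daunorubicin schedule: in Appendix 2, Table 1, Induction Cycle 1 Day 5, tie the early sample to the idasanutlin dose in both the idasanutlin and MIC-1 columns.

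The natural time for the sponsor to confirm is 1.5 h (±10 min). For idasanutlin the precedent is Day 5 of consolidation and maintenance. For MIC-1 it cannot be those days, which have no MIC-1 sample. It is Induction Day 3, set at "1.5 hr (±10 min) post-idasanutlin administration".

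This changes a sampling time only, not dosing. It costs one row in Appendix 2 and a matching entry in the laboratory manual. The number of blood draws stays the same. If patients have already passed Day 5, the analysis should use actual sampling times and report how many early samples were missing.

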Appendix 2: Schedule of Pharmacokinetic and PD Biomarker Samples (cont.)

Table 1 All Cohorts (cont.)

| Study Visit | | Plasma Idasanutlin PK Sample | Serum MIC-1 Sample | Plasma Cytarabine PK Sample | Plasma Daunorubicin PK Sample |
|--|-------|---|--------------------|---|-------------------------------|
| Consolidation Cycle 1 (cont.) | Day 5 | Pre-idasanutlin administration (any time prior to dose on that day) | | Pre-idasanutlin administration (any time prior to dose on that day) | |
| | | 1.5 hr (± 10 min) post-idasanutlin administration | | 1.5 hr (± 10 min) post-idasanutlin administration | |
| | | 3 hr (± 10 min) post-idasanutlin administration | | 3 hr (± 10 min) post-idasanutlin administration | |
| | | 6 hr (± 20 min) post-idasanutlin administration | | 6 hr (± 20 min) post-idasanutlin administration | |
| | | 9 (± 1) hr post-idasanutlin administration | | 9 (± 1) hr post-idasanutlin administration | |
| Maintenance Cycle 1 (expansion and post-consolidation) | Day 1 | Pre-idasanutlin administration (any time prior to dose on that day) | | | |
| | | 6 hr (± 20 min) post-idasanutlin administration | | | |

PK=pharmacokinetic.

Appendix 2: Schedule of Pharmacokinetic and PD Biomarker Samples (cont.)

Table 1 All Cohorts (cont.)

| Study Visit | | Plasma Idasanutlin PK Sample | Serum MIC-1 Sample | Plasma Cytarabine PK Sample | Plasma Daunorubicin PK Sample |
|--|-------|---|--------------------|-----------------------------|-------------------------------|
| Maintenance Cycle 1 (expansion and post-consolidation) (cont.) | Day 5 | Pre-idasanutlin administration (any time prior to dose on that day) | | | |
| | | 1.5 hr (± 10 min) post-idasanutlin administration | | | |
| | | 3 hr (± 10 min) post-idasanutlin administration | | | |
| | | 6 hr (± 20 min) post-idasanutlin administration | | | |
| | | 9 (± 1) hr post-idasanutlin administration | | | |

PK=pharmacokinetic.

Appendix 3

Eastern Cooperative Oncology Group Performance Status Scale

| Grade | Description |
|-------|---|
| 0 | Fully active, able to carry on all pre-disease performance without restriction |
| 1 | Restricted in physically strenuous activity but ambulatory and able to carry out work of a light or sedentary nature, for example, light housework or office work |
| 2 | Ambulatory and capable of all self-care but unable to carry out any work activities. Up and about > 50% of waking hours |
| 3 | Capable of only limited self-care, confined to a bed or chair > 50% of waking hours |
| 4 | Completely disabled. Cannot carry on any self-care. Totally confined to bed or chair |
| 5 | Dead |

Appendix 4

Howard Definition and Classification of Tumor Lysis Syndrome (Howard et al. 2011)

| Definitions of Laboratory and Clinical Tumor Lysis Syndrome ^a | | |
|--|---|--|
| Metabolic Abnormality | Criteria for Classification of Laboratory Tumor Lysis Syndrome | Criteria for Classification of Clinical Tumor Lysis Syndrome |
| Hyperuricemia | Uric acid > 8.0 mg/dL (475.8 μmol/L) in adults or above the upper limit of the normal range for age in children | |
| Hyperphosphatemia | Phosphorus > 4.5 mg/dL (1.5 mmol/L) in adults or > 6.5 mg/dL (2.1 mmol/L) in children | |
| Hyperkalemia | Potassium > 6.0 mmol/L | Cardiac dysrhythmia or sudden death probably or definitely caused by hyperkalemia |
| Hypocalcemia | Corrected calcium < 7.0 mg/dL (1.75 mmol/L) or ionized calcium < 1.12 (0.3 mmol/L) ^b | Cardiac dysrhythmia, sudden death, seizure, neuromuscular irritability (tetany, paresthesias, muscle twitching, carpopedal spasm, Trousseau's sign, Chvostek's sign, laryngospasm, or bronchospasm), hypotension, or heart failure probably or definitely caused by hypocalcemia |
| Acute kidney injury ^c | Not applicable | Increase in the serum creatinine level of 0.3 mg/dL (26.5 μmol/L) (or a single value > 1.5 times the upper limit of the age-appropriate normal range if no baseline creatinine measurement is available) or the presence of oliguria, defined as an average urine output of < 0.5 mL/kg/hr for 6 hours |

^a In laboratory tumor lysis syndrome, two or more metabolic abnormalities must be present during the same 24-hour period within 3 days before the start of therapy or up to 7 days afterward. Clinical tumor lysis syndrome requires the presence of laboratory tumor lysis syndrome plus an increased creatinine level, seizures, cardiac dysrhythmia, or death.

^b The corrected calcium level in milligrams per deciliter = measured calcium level in milligrams per deciliter + 0.8 × (4 – albumin in grams per deciliter).

^c Acute kidney injury is defined as an increase in the creatinine level of at least 0.3 mg/dL (26.5 μmol/L) or a period of oliguria lasting 6 hours or more. By definition, if acute kidney injury is present, the patient has clinical tumor lysis syndrome. Data about acute kidney injury are from Levin et al. (2007).

Appendix 5 Toxicity Management Guidelines

DIARRHEA MANAGEMENT GUIDELINES AND RECOMMENDATIONS

Diarrhea has been the most frequently reported adverse event in patients with acute myeloid leukemia (AML) administered with idasanutlin (Study NP28679).

Prior to first study medication administration

Patients should be carefully screened for active GI conditions (e.g., graft-versus-host disease, $G \geq 2$) and uncontrolled irritable bowel disease (i.e., Crohn's disease, ulcerative colitis, diverticulosis-associated colitis, and Behçet disease) prior to enrollment. Patients with active GI conditions as noted in the exclusion criteria are not permitted to start treatment.

Establish the individual patient's normal bowel function. Discuss how function could change in the future with treatment. Discuss dietary management/rehydration.

Prophylactic antidiarrheal therapy is to be instituted for all patients administered study medications in induction and consolidation as follows (unless medically contra-indicated):

Loading dose of loperamide 4 mg orally 30 minutes before first administration of idasanutlin

Instruct patients on warning signs (e.g., bloody stools, associated fever, and dizziness).

- **Event management**

Should diarrhea occur: administer loperamide 2 mg orally every 4 hours or after every unformed stool to a maximum dose of 16 mg/24 hr.

Rule out other or concomitant causes, including medications (e.g., stool softeners, laxatives, and antacids), *C. difficile* infection (CDI), malabsorption/lactose intolerance, fecal impaction, and dietary supplements high in fiber

Dietary measures: Discontinue all lactose-containing products, alcohol and high-osmolar supplements; instruct patients to eat frequent small meals (e.g., bananas, rice, apples, and toast).

Loperamide treatment should be continued until patient is diarrhea-free for ≥ 24 hours or until Day 10 of the specific cycle, whichever occurs first.

Record the number of stools and report complications (e.g., fever or dizziness upon standing).

Encourage adequate hydration.

Monitor electrolytes daily (i.e., potassium, magnesium, calcium, and sodium).

Administer IV fluids as clinically indicated and aim at all times for electrolyte correction.

Appendix 5: Toxicity Management Guidelines (cont.)

Table 1 Diarrhea Management According to CTCAE Grade

| Diarrhea Grade | Recommended Actions |
|----------------|---|
| Grade 1/2 | 
a) See all supportive recommendations indicated above (i.e., loperamide, symptomatic management, dietary counselling, rehydration, and electrolyte correction).b) No change in study medication dose will be implemented for Grade ≤ 2 diarrhea; patients should receive maximal supportive care as described above.c) If diarrhea persists after 48 – 72 hours despite administration of the maximum recommended daily loperamide dose (16 mg/24 hr), second-line agents may be considered. |
| Grade 3 | 
d) Consider second-line agents (i.e., diphenoxylate, atropine, octreotide, budesonide, or tincture of opium) if the patient is receiving loperamide at the maximum recommended daily dose (16 mg/24 hr).e) If no improvement is observed within 24 hours, test for CDI.f) If, despite adequate supportive care, Grade 3 diarrhea persists >48 hours without responding to loperamide at the maximum recommended daily dose (16 mg/24 hr), the idasanutlin dose should be reduced as per Table 11.g) If clinical characteristics have NOT improved to Grade ≤ 1 or baseline by 28 days despite the patient receiving maximal supportive care, idasanutlin must be permanently discontinued.h) If the diarrhea recurs at Grade 3 despite supportive care and idasanutlin dose reduction, idasanutlin must be permanently discontinued. |
| Grade 4 | 
i) If, despite prophylaxis and adequate supportive care, Grade 4 diarrhea is diagnosed, idasanutlin must be permanently discontinued.j) Consider second-line agents (i.e., diphenoxylate, atropine, octreotide, budesonide, or tincture of opium) if the patient is currently receiving loperamide at the maximum recommended daily dose (16 mg/24 hr).k) If no improvement is observed within 24 hours, test for CDI. |

CDI = *Clostridium difficile* infection; CTCAE = Common Terminology Criteria for Adverse Events.

CLOSTRIDIUM DIFFICILE INFECTION

Due to the high incidence of diarrhea, CDI may occur undetected. Once diagnosed, monitoring CDI is also challenging, as treatment-induced diarrhea may be persistent. The risk factors for CDI are common in this patient population (treatment with systemic

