5.1.3.1.1 Non-Hematologic Toxicities

Guidelines for management of non-hematologic toxicities that occur during induction and consolidation treatment are presented in [Table 10](#) and [Table 11](#).

Table 10 Guidelines for Management of Idasanutlin-Related Gastrointestinal Toxicities in Induction and Consolidation

| Event | Action to Be Taken |
|----------|--|
| Diarrhea | 
Permanently discontinue study treatment for Grade 4 events.
 
Grade 3 diarrhea:
 
• If Grade 3 diarrhea occurs between Days 1 and 5 of the treatment cycle, withhold idasanutlin only if diarrhea does not improve to Grade ≤ 2 within 72 hours with appropriate treatment. After the study treatment is withheld, if diarrhea improves to Grade ≤ 2, resume idasanutlin at a reduced dose according to guidelines in Sections 5.1.3 for current and subsequent cycles. |
| Vomiting | 
Grade 4 vomiting:
 
• Permanently discontinue study treatment. 
Grade 1, 2, or 3 vomiting:
 
• If vomiting occurs within 15 minutes of taking idasanutlin, and all expelled tablets are still intact, another dose may be given and the second dose noted in the drug log. Otherwise, no replacement dose is to be given (see Section 4.3.2). |

Table 11 Guidelines for Management of Idasanutlin-Related Non-Hematologic Toxicities in Induction and Consolidation

| Event | Action to Be Taken |
|--|---|
| 
 General guidance for treatment delays, discontinuation, and resumption | 
 If study treatment is withheld for >21 days because of a toxicity that is attributable to study treatment, permanently discontinue study treatment. Permanently discontinue study treatment for Grade 4 events. Dosing may be resumed after resolution to Grade ≤ 2 or baseline status. Resumption of dosing without complete resolution of toxicity may be considered in special circumstances after having obtained Medical Monitor agreement. |
| IRRs and anaphylaxis | 
 Guidelines for the management of IRRs are provided in Appendix 5. In case of Grade 4 IRRs or anaphylaxis, study treatment should be permanently discontinued. |

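### For Grade 3 diarrhea in induction and consolidation, Appendix 5 and Section 5.1.3 differ on when idasanutlin is permanently stopped, and neither is said to govern

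*Combined protocol and SAP*

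**What the plan says.** Two parts of the protocol tell a site what to do about Grade 3 diarrhea in induction and consolidation.

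Appendix 5, Table 1 (diarrhea by CTCAE grade), Grade 3 row:
- Item f, for Grade 3 diarrhea that persists despite supportive care: "the idasanutlin dose should be reduced as per Table 11".
- Item g: "improved to Grade ≤ 1 or baseline by 28 days despite the patient receiving maximal supportive care, idasanutlin must be permanently discontinued" (the condition being failure to reach that state).
- Item h: "If the diarrhea recurs at Grade 3 despite supportive care and idasanutlin dose reduction, idasanutlin must be permanently discontinued".

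Section 5.1.3 and its tables:
- Table 10, diarrhea on Days 1–5: "withhold idasanutlin only if diarrhea does not improve to Grade ≤ 2 within 72 hours with appropriate treatment". After a hold, "if diarrhea improves to Grade ≤ 2, resume idasanutlin at a reduced dose", for the current and later cycles, following Section 5.1.3. There is no rule for recurrence.
- Table 8, in Section 5.1.3, lists the reduction steps. Its footnote discontinues study drug when no further reduction is possible.
- Table 11, general guidance row, lets dosing resume at Grade 2 or less or baseline, and adds: "If study treatment is withheld for >21 days because of a toxicity that is attributable to study treatment, permanently discontinue study treatment".

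Section 5.1.1.1 sends the reader to both Section 5.1.3.1 and Appendix 5 for gastrointestinal events. Section 5.1.3 also refers to both. Neither says which prevails.

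**The concern.** A permanent stop is the most consequential action in these tables, because the patient also loses idasanutlin for any remaining induction or consolidation cycles and for maintenance. If the recovery grade and the recurrence rule differ between two pages that both apply, the outcome depends on which page the site opens.

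This bears on patient safety and on planned outputs. Section 6.4 reports adverse events leading to discontinuation, cycles started and cumulative dose, and Section 5.2.3 makes Grade 2 or worse diarrhea an event of special interest. The study is non-randomized, and each expansion cohort has 20 patients. One patient whose stop depends on the page read therefore moves a cohort's discontinuation proportion by 1/20 = 5 percentage points.

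**Working it through.** The plan states no figure to reproduce. The check sets the rules side by side and runs hypothetical patients through each.

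**1. Recovery grade.** Item g needs Grade 1 or less, or baseline. Table 10 needs Grade 2 or less, and the Table 11 general row needs Grade 2 or less or baseline. The baseline alternative in item g does not close the gap: Section 4.1.2.1 excludes Grade 2 or worse non-hematologic toxicity before therapy (apart from fatigue, anorexia and alopecia), so baseline diarrhea is Grade 1 at most.

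Patient A has Grade 3 diarrhea for 96 hours, is withheld for no more than 21 days, settles at Grade 2 and is still Grade 2 at day 28. Table 10 resumes at a reduced dose. Item g stops the drug permanently.

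**2. Recurrence.** Doses after each Table 8 step, by subtraction:
- 150 mg: 100 (one step)
- 200 mg: 150, 100 (two steps)
- 250 mg: 150, 100 (two steps)
- 300 mg: 200, 150, 100 (three steps)
- 350 mg: 250, 150, 100 (three steps)
- 400 mg: 300, 200, 150 (three steps)

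These are total steps. After the first reduction, one remains from 200–250 mg and two from 300–400 mg.

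Patient B has been reduced once, from 200 mg or more. Grade 3 recurs, lasts 96 hours and improves to Grade 2. Tables 10 and 8 resume at the next step (for a 300 mg starter now on 200 mg, that is 150 mg, with 100 mg still below it). Item h stops the drug.

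Patient C has the same history, but the recurrence clears in 24 hours. Table 10 does not even withhold, because the 72-hour condition is not met. Item h, read literally, stops the drug.

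From 150 mg the Patient B conflict does not arise, since the single step is already used. The induction starting dose is 200 mg.

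**3. Cross-reference.** Item f points to Table 11 for the reduction. Table 11 has no diarrhea row. Its Grade 3 reduction row covers toxicities not listed elsewhere. Diarrhea is in Table 10 and the steps are in Table 8.

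**4. Time limits.** Table 11 counts days that study treatment is withheld (more than 21). Item g counts to 28 days, gives no start point and looks at the state of the diarrhea. A patient withheld for 24 days and at Grade 1 on day 25 meets the Table 11 stop but not item g.

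**5. How many patients.** The only rate in the documents is Table 7's 13% for Grade 3 or worse diarrhea with idasanutlin. Assumed induction base: 9 + 40 = 49 to 20 + 40 = 60. Then 0.13 × 49 = 6.4 and 0.13 × 60 = 7.8. Section 6.1 counts escalation patients at the RP2D within the 20 favorable/intermediate patients, so 49 is not a firm minimum.

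**The case against.** The best defence is that Appendix 5 adds to Table 10 and does not contradict it. Table 10 is silent on recurrence and defers to Section 5.1.3, which cites Appendix 5. Table 8 gives step sizes by which the dose may be reduced, and does not entitle a patient to every step. On this view a site reduces once and then applies items g and h as further stops. Section 5.1.3 also says that toxicities subsiding before the next cycle should not trigger dose modifications, and it allows sponsor-reviewed exceptions.

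Part of this stands: the recurrence conflict is less direct than the recovery-grade conflict, and fewer patients reach item h than have Grade 3 diarrhea. It does not remove either conflict. Table 10 resumes withheld Grade 3 diarrhea at Grade 2 or less without distinguishing a first episode from a later one, and Table 8's footnote ties discontinuation to having no step left. Gap-filling cannot explain the recovery grade, where both sources speak. Case-by-case exceptions do not say which default applies, and items g and h are worded as mandatory.

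Three stronger readings are tempting but unsupported:
- A reader might infer that 21 and 28 days contradict each other. Both are sufficient conditions for stopping, on different clocks, and neither tells a site to continue. They can be applied together, whichever is met first.
- A reader might infer that ending loperamide when diarrhea-free "or until Day 10 of the specific cycle, whichever occurs first" defeats item g's supportive-care condition, or blocks the gastrointestinal DLT criterion. Supportive care in Appendix 5 also includes diet, hydration, electrolyte correction and second-line agents, none of which has a Day 10 limit. The DLT definition in Section 3.1.2.1 does not require loperamide.
- A reader might take 6–8 as the number of patients affected. The documents do not support that, for the reasons given in the verdict.

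**Conclusion.** The concern holds in this form. For Grade 3 diarrhea in induction and consolidation, Appendix 5 items g and h permanently stop idasanutlin in patients whom Tables 8 and 10 would re-dose, item f cites the wrong table, and no precedence is stated. The recovery-grade conflict is firm. The recurrence conflict is real but rests on reading Tables 8 and 10 together. The time limits are a secondary matter of alignment. The direction is mixed: Appendix 5 is stricter on recovery grade and recurrence, while its 28 days is the longer figure.

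The number affected is unknown, because the documents give no rate for diarrhea that persists to 28 days or recurs at Grade 3 after a reduction. The 6–8 patients are an assumed pool with any Grade 3 or worse diarrhea. The 13% is pooled over solid-tumor and relapsed or refractory AML studies, and it includes Grade 4, where both sources stop. No effect on the CR estimate is shown. This is a wording inconsistency with consequences for safety management and discontinuation data, and should be corrected.

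**What to change.** Reconcile Appendix 5 items f–h with Tables 8, 10 and 11 so that one recovery grade, one recurrence rule and one time limit apply to Grade 3 diarrhea in induction and consolidation. State when the time limit starts and what it counts. Correct the Table 11 reference in item f. Add a sentence in Section 5.1.3 saying which passage governs if the main text and Appendix 5 differ. Which values stand is for the clinical team. The cost is protocol wording only, with no added visits, samples or patients.
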